2. OBJECTIVES AND HYPOTHESIS

2.1. Definitions

Clinical resolution is a clinical definition, resulting from a slit lamp examination, with the following findings:

- No corneal inflammation (including subepithelial infiltrates, stromal infiltrates and oedema) that requires treatment, with a healed corneal epithelium and minimal punctate staining (10 dots or less equivalent to Grade 1 on the Oxford Scale).
- No or mild conjunctival inflammation (including bulbar injection, bulbar oedema, tarsal hyperemia): mild conjunctival inflammation is acceptable if related to other concurrent conditions such as blepharitis.
- No limbitis, scleritis or anterior chamber inflammation.
- No relapse within 30 days of discontinuing all topical and systemic therapy given for *Acanthamoeba* keratitis.

For regulatory and verification reasons there is an additional 60 day follow-up to exclude late relapses.

The CRR_12 is the clinical resolution rate at 12 months from randomization and is defined as the percentage of subjects cured 30 days after discontinuing all study therapies, within 12 months of randomization. This is the primary outcome measure. Subjects whose disease has not resolved at 12 months are considered treatment failures per protocol.

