6.3. Primary Efficacy Variables

The primary efficacy variable chosen to assess drug efficacy is the CRR_12 (the clinical resolution rate at 12 months from randomization, defined as the percentage of subjects cured 30 days after discontinuing all study therapies, within 12 months of randomization).

Criteria for clinical resolution:

A subject will be considered cured if resolution of all the following clinical signs are observed, resulting from a slit lamp examination:

- No corneal inflammation (including subepithelial infiltrates, stromal infiltrates and oedema) that requires treatment, with a healed corneal epithelium and minimal punctate staining (10 dots or less equivalent to Grade 1 on the Oxford Scale).
- No or mild conjunctival inflammation (including bulbar injection, bulbar oedema, tarsal hyperemia): mild conjunctival inflammation is acceptable if related to other concurrent conditions such as blepharitis.
- No limbitis, scleritis or anterior chamber inflammation.

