7.1.3 Analysis Relative Day

The analysis relative day for an assessment/value is defined as the time in days from the date of randomization to the date of the assessment. The date of randomization is considered as day 1, and earlier dates will correspond to a negative day. In the Schedules of assessments table on page 22 and 23 of the protocol, the day of randomisation, which also encompass some baseline measurements and drug dispensing, is called Day 0. As CDISC does not use 0 for day numbering, Day 1 will be used for the day of randomisation. Hence, the day numbering after the baseline day in the Schedules table will be increased by one.

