7.2.1 Full Analysis Set (FAS)

All subjects who have been randomized and has a confirmed diagnosis of Acanthamoeba keratitis and for whom the primary efficacy variable has been assessed will be included in the FAS. The FAS will be used in all efficacy analyses. The last disease status assessment will be used for disease status assessment.

Analysis using the FAS will be based on the planned treatment (i.e. subjects will be analysed 'as randomised').

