7.2.2 Per-Protocol Analysis Set (PPAS)

The per-protocol analysis set is defined as the subset of subjects in the FAS for whom no major protocol deviation judged as having an impact on the primary efficacy analysis was reported or identified. The last disease status assessment within 12 months of randomisation will be used for disease status assessment. For subjects with disease resolution at that last visit, the 30-day and 90-day follow-up assessments should confirm disease resolution. Otherwise, the disease will be regarded as not having been resolved.

The decision as to which protocol deviations should be considered as reason for exclusion from the PPAS should be made at the clean file meeting and documented in the clean file report.

Analysis on the PPAS will be based on the actual treatment (i.e. subjects will be analysed 'as treated'). The primary efficacy variable, CRR_12, will also be evaluated using the PPAS.

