7.9.1 Primary Efficacy Variable

The main endpoint disease resolution 12 months after baseline will be assessed at each visit up to study day 365.

Clinical resolution 12 months after baseline for a patient is defined as:

The percentage of subjects cured 30 days after discontinuing all study therapies, within 12 months of randomization. A clinical resolution classification requires a Yes response to the eCRF variable CRYN question: "Was clinical resolution obtained?" at one of the study visits from day 1 up to study day 365 in combination with a response *No* to the eCRF variable RELAPYN question "Did the subject experience relapse since the last visit?" at the pursuing visits, up to the last recording of this information. There should be no relapses after (the last) clinical resolution classification. Discontinued subjects will be regarded as not cured.

For patients defined as fulfilling disease resolution within 12 months, the date of the visit at which annotated CRYN is first answered with a Yes will be used as the date of resolution. The time-to-cure secondary variable will be the number of days from randomisation to the visit where resolution was recorded.

Since it is also possible to test for non-inferiority if the superiority hypothesis is not met, additional conditions are specified (see list below) to meet the strict requirements of a non-inferiority study, making it feasible to test for non-inferiority using the results from the superiority analysis, without a further separate analysis. The 90% CI for the difference between the treatments obtained from the superiority analysis gives the necessary information. Position of the lower end of the CI relative to a pre-defined agreed 0.20 non-inferiority margin (Δ) provides the key information for making decisions (conclusions) about non-inferiority.

PHMB has received the orphan drug designation. The use of 90% CI for the difference between the two treatments is to provide a 95% lower CI limit for non-inferiority.

The additional conditions specified to make testing for non-inferiority feasible are the following:

- Pre-defined non-inferiority margin (Δ =0.20) based on both clinical and statistical considerations, i.e., chosen on the basis of external information and not chosen to fit the data.
- Analysis of the FAS and the PPAS, giving similar results with respect to p-values and CIs for the
 efficacy measure at issue.

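### The cure status behind CRR_12 is derived by different relapse windows and time limits in the protocol definition, SAP 7.9.1, the FAS rule and the PPAS rule

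*SAP*

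**What the plan says.** **Protocol definition.** Protocol 6.3 defines CRR_12 as the "percentage of subjects cured 30 days after discontinuing all study therapies, within 12 months of randomization". Protocol 2.1 includes among the criteria for resolution "No relapse within 30 days of discontinuing all topical and systemic therapy given for" the disease, and sets the later period apart: "For regulatory and verification reasons there is an additional 60 day follow-up to exclude late relapses". SAP 3.1, 3.2.1 and 6.1 repeat the 30-day criterion.

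**Protocol success pathway.** Boxes VI and VII in Protocol 5.3.1 assign treatment success only when there is no sign of relapse at the visit 90 days after the last treatment, by Day 455 at the latest.

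**SAP 7.9.1.** A subject is resolved if the resolution question (CRYN) is answered Yes at a visit up to study day 365 and the relapse question is answered No "at the pursuing visits, up to the last recording of this information". No relapse may follow the last resolution. Discontinued subjects count as not cured.

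**SAP 7.2.1 (FAS).** "The last disease status assessment will be used for disease status assessment", with no time limit.

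**SAP 7.2.2 (PPAS).** The last status within 12 months is used. For subjects resolved at that point, "the 30-day and 90-day follow-up assessments should confirm disease resolution"; failing that, the disease counts as unresolved.

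**SAP 7.1.3.** Randomisation becomes Day 1: "Hence, the day numbering after the baseline day in the Schedules table will be increased by one".

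**The concern.** This is the primary endpoint, and the text gives a programmer several rules that do not agree. They differ in how long a subject must stay relapse-free (30 days, to the last record, or both Day 30 and Day 90) and in the time limit (12 months, study day 365, or none).

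SAP 7.9.1 makes similar results in the FAS and PPAS a condition for claiming non-inferiority. That comparison is informative only if the two sets differ in who is included. If cure is also derived differently, agreement or disagreement may come from the rule and not from protocol deviations.

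SAP section 2 says that changes to principal features belong in a protocol amendment as well. SAP 7.11 reports no planned changes beyond an altered PPAS definition, so the longer relapse window in 7.9.1 is not declared as a change to the endpoint.

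**Working it through.** **Scale.** The plan's sample size (Protocol 7.6, SAP 5.1) gives the number per arm. Inputs are control 0.63, test 0.63 + 0.20 = 0.83, one-sided alpha 0.05, 80% power and 10% loss. With unpooled variance:

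- n per arm = (1.645 + 0.842)² × (0.63×0.37 + 0.83×0.17) / 0.20² = 6.183 × 0.3742 / 0.04 = 57.8, so 58 (116 evaluable).
- 58 / 0.90 = 64.4, so 65 per arm and 130 in total. Both figures match the plan.
- Power at 58 per arm: 0.20 / √(0.3742/58) − 1.645 = 0.845, which is 80.1%.
- One reclassified subject moves an arm's CRR_12 by 1/58 = 1.7 points (1/65 = 1.5 points if all randomised subjects are counted).

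**Rules applied to constructed subjects.** The days are illustrative.

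| Subject | Protocol 30-day definition | Protocol Boxes VI/VII | SAP 7.9.1 | SAP 7.2.1 (FAS) | SAP 7.2.2 (PPAS) |
|---|---|---|---|---|---|
| A. Stops day 200; clear at Day 30; relapse found at Day 90; does not resolve again | cured | failed | failed | failed | failed |
| B. Stops day 200; clear at Day 30; no Day-90 record | cured | not confirmed | cured (a) | cured | failed (b) |
| C. Unresolved at day 365; first resolved at a later recorded assessment, e.g. day 370 | failed | failed | failed | cured | failed |
| D. Stops day 200; clear at Day 30 and Day 90 | cured | cured | cured | cured | cured |

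(a) Not cured if the missing visit makes the subject discontinued. (b) Removed instead of failed if the missing visit is ruled a major deviation under SAP 7.4.

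**What the table shows.**

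- A separates the protocol's 30-day definition from every SAP rule and from the protocol's own success boxes. It does not separate FAS from PPAS.
- B can separate FAS from PPAS.
- C separates them only if 7.2.1 overrides the day-365 limit in 7.9.1. The SAP does not say which of these two sections governs.

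**Day numbering.** Box IV accepts resolution at or before 365 days from study entry. With randomisation as Day 1, protocol Day 365 is study day 366, one day outside the 7.9.1 limit as written. The visit-window table in SAP 7.1.4 keeps the unshifted days, so it is unclear which numbering the 365 in 7.9.1 uses. Only a visit on exactly that day is affected.

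**The case against.** **The conflict starts in the protocol.** Boxes VI and VII tie success to Day 90. Protocol 5.3.4 counts as a clinical failure a relapse within 3 months after end of treatment if it occurs more than 12 months after randomisation. SAP 7.9.1 can be read as following that pathway. This stands. A reader might infer that neither analysis set measures what the protocol intended, or that Day 90 must be demoted, and the documents support neither.

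**A late relapse is not always a failure.** A reader might infer that any relapse between Day 30 and Day 90 fails under 7.9.1. But that section looks only at relapses after the last resolution, and note 3 to the Schedule of Assessments restarts treatment after a culture-negative relapse within 11 months. Such a subject can resolve again and count as cured. Example A therefore specifies no second resolution.

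**Resolution on, say, day 350.** A reader might infer that the SAP wrongly counts this subject as cured, because 30 days off therapy would end after 12 months. The documents do not support that as an error. The protocol's abbreviation list can be read as limiting when therapy stops, Box IV allows stopping up to day 365, and Day 455 is 365 + 90. The limit is ambiguous, and that is all that can be said.

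**FAS/PPAS splits may be rare.** Protocol 4.4 requires the 90-day assessments for completion, SAP 7.3 counts leaving before the follow-up visits as premature withdrawal, and SAP 7.4 lists not attending the two follow-up visits as a major deviation. The protocol also exits subjects still unresolved at day 365 as failures. These rules may remove many B and C cases. However, the SAP does not state how a single missed Day-90 visit is classed.

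**Conclusion.** The inconsistency is real and lies in current text. The firm result is example A: a subject clear at Day 30 who relapses by Day 90 and does not resolve again is cured under the protocol definition and failed under the SAP. On the literal text, FAS and PPAS can also disagree for a subject with no Day-90 record or one first resolved after day 365. Such subjects are probably few, and the discontinuation and major-deviation rules may cover some of them.

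The total effect cannot be derived, because the documents give no rate of late relapse, missed Day-90 visits or post-365 resolution. All that can be given is 1.7 points per reclassified subject at 58 per arm, in a design with 80.1% power on its own assumptions. No difference between arms is shown. A reader might infer that the FAS and PPAS results will diverge materially, and nothing in the documents establishes that. The sample size itself is not in error.

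**What to change.** 1. Delete the disease-status sentences from SAP 7.2.1 and 7.2.2, including the PPAS confirmation rule. The two sets then differ only in membership.
2. Put one cure derivation in SAP 7.9.1 and apply it to both sets. State how a missing Day-30 or Day-90 visit is classed.
3. Reconcile the 30-day definition (Protocol 2.1 and 6.3, SAP 3.1 and 6.1) with the Day-90 success rule in Boxes VI and VII. Name one as primary and report the other as a sensitivity analysis. If the primary is not the 30-day definition, record this in a protocol amendment, as SAP section 2 requires.
4. State whether the 12-month limit applies to stopping therapy or to the 30-day check, and give it in SAP day numbering (protocol Day 365 = study day 366).

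The cost is SAP wording and one sensitivity table, plus an amendment if Day 90 is chosen. No new data are needed. The change should be made before the code is broken.

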- 3. If within 90 days after end-of-treatment and within 11 months (Day 335) after randomization the subject relapses, and cultures are negative for *Acanthamoeba*, treatment with the study drug will be re-started according to the treatment schedule, starting with the Day 0 treatment regime. Assessments and visits will also be restarted at Day 0, Day 30 and all consecutive visits of the treatment phase. A detailed treatment plan and follow-up protocol is provided in Section 5.3.
- 4. End-of-study is defined as: (a) the last follow-up visit at 90 days after end of treatment, (b) the day of study drug unmasking in the event of the subject becoming a Treatment failure, (c) if withdrawn from the trial of other reasons, (d) if a subject has been treated for 12 months after randomization (also a Treatment failure).
- 5. Screening and baseline assessments will take place on Day -2 to 0, before randomization and study drug administration.
- 6. For subjects who have not reached the age of majority (i.e. 18 years of age in most jurisdictions), the subject must provide assent (written or verbal) and the parent/guardian/legally authorized representative must provide written informed consent before the subject's participation in the study.
- 7. All medical and medication history related to the current eye infection will be reported. For the remaining medical and medication history, only the last 30 days before signing the ICF will be reported in the case report form (CRF).
- 8. Confocal microscopy is optional if already performed within 7 days prior to study entry as part of standard care providing the images are available to the Investigator to assess.

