5.3.3. Relapse

BOX XI RELAPSE WITHIN 11 MONTHS

Relapse within 11 months, after an initial response is common. Cultures for *Acanthamoeba* and other organisms (fungi, bacteria and herpes) must be repeated, deriving from a repeated corneal biopsy, if the investigator thinks this is appropriate.

- c. If the CULTURES are NEGATIVE patients this may mean that the anti-amoebic therapy is having some effect although we have no way of being certain about this (confocal and PCR don't help as these can be positive when the organisms are non-viable). These patients are managed as described in XIII below with another 19 day course of intensive therapy, with or without anti-inflammatory therapy depending on status.
- d. If CULTURES are POSITIVE patients have TREATMENT FAILURE and managed as described in XIV and XVII below.

Box XII. EXACERBATION of inflammation is presumed to be due to inflammation secondary to the immune response to non-viable Acanthamoeba and anti-inflammatory treatment can be re-started or increased at the discretion of the PI without the need for re-culture and a further course of intensive anti-amoebic therapy. IMPORTANT: if anti-amoebic treatment had been stopped restart this when anti-inflammatory treatment is re-started.

Distinguishing between XI and XII is often difficult and guidelines for this are given in II a, b above.

Box XIII. Restart with another 19 day intensive course of anti-amoebic therapy with or without topical steroids and oral NSAIDS:

- a. If patients were not on these at the time of the relapse of infection we recommend not using these until after the 19 day course of intensive treatment and depending on response move to as above.
- b. If they were on them at the time of the relapse continue at a dose determined by the PI and follow pathways II, III, IX or X.

Box XIV. CULTURE POSITIVE these patients are Exit Trial and are managed as described in XVII below.

Box XV. SCLERITIS UNRESPONSIVE to treatment in IX. This is a failure (see XVII below).

Box XVI. RELAPSE after day 335 or ingoing inflammation and treatment at day 365: this is a treatment failure and is managed as described in XVII below

Box XVII. TREATMENT FAILURE and EXIT TRIAL. The treatment randomization allocation will be opened by the Sponsor at this point. Trial drug (PHMB 0.08%) will be available to the patient, if requested by the Investigator, providing the patient continues trial follow up for safety evaluation.

XVIII. Summary of Study end points.

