7.1.7 Multiplicity

Three hypotheses are specified in the Protocol, one primary and two secondary hypotheses. Time-to-resolution using the visit day at which resolution was first seen, will be considered statistically significant if the sum of the p-value for the primary variable and the p-value from the time-to-resolution analysis is less than the specified overall significant level. The use of a non-inferiority alternative if the difference alternative should not be obtained, does not affect the overall p-value level of the primary hypothesis.

Hypotheses tested for other secondary variables will all be analysed using significance elves of 0.05.

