7.2 Analysis Sets

The decision on the classification of subjects to each analysis set will be taken at the clean file meeting, prior to breaking the blind, and documented in the clean file report together with the reasons for excluding subjects from analysis sets. Subjects who have not attended any visits where disease status is assessed, i.e. those who did not reach the day 30 visit, the first visit where disease status is recorded, will be classified as dropouts from the efficacy analysis sets. Any 30dayFU visit that is under the window, i.e. visit occurred too soon, will not be removed from the analysis population as long as the 90DayFU visit also proved that the patient was cured.

LINK Medical Study ID: PSR012

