7.9.3 Secondary Efficacy Variables¹

Time-to-cure comparison between the treatment groups is specified as efficacy hypothesis and will be subjected to formal statistical testing. Other analyses of secondary efficacy variables will be done on a hypothesis-generating basis, i.e. no p-value adjustments will be conducted, and conclusions regarding the analysis results will be commented on such a basis.

Time-to-cure

The aim of the hypothesis test is to show that the time is less among the subjects receiving PHBM 0.08% monotherapy compared to the comparator. Patients will either be classified as Cured at some point of time while in the study or leave the study without being classified as Cured. As a secondary efficacy variable, timeto-cure (clinical resolution) will be analysed. The Cox Proportional Hazards regression (subject to validity of the 'proportional hazards' assumption) and Kaplan-Meier survival plots. If the proportional hazard assumption is not fulfilled a logrank test will be performed. Not all patients may have information regarding when they were cured, e.g. due to death before being cured, or completed the study without being cured. Both the Cox Proportional Hazards regression and the Kaplan-Meier plot uses the censoring timepoint in their calculations. The censoring timepoint will be defined based on the timepoint of the last observation when cure status was assessed. The null hypothesis is that the two treatment arms have equal hazard functions. Relevant data will be presented at the Clean file meeting for discussion and acceptance.

BCVA

The VAMS states that: "Depending on the problem, this notation can be most useful when analysing or graphically plotting visual acuity scores because equal linear steps on the LogMAR scale represent equal ratios in the standard size sequence." Hence, BCVA will be presented and analysed using LogMAR values, where

$$LogMAR = \log \left(\frac{ORRES_{BCA2}}{ORRES_{BCA1}} \right),$$

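### Time-to-cure is judged on the last resolution but dated at the first, and the sum-of-p rule that tests it names no significance level

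*SAP*

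**What the plan says.** **Success and its date.** SAP 7.9.1 requires a Yes to CRYN at a visit up to day 365, No to RELAPYN afterwards, and no relapse after the last resolution classification. SAP 7.2.1 points the same way: "The last disease status assessment will be used for disease status assessment". The date is taken from the other end. Under 7.9.1, for subjects who meet the 12-month definition, "the date of the visit at which annotated CRYN is first answered with a Yes will be used as the date of resolution". SAP 7.1.7 repeats this: "using the visit day at which resolution was first seen".

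**Why first and last can differ.** Note 3 to the Protocol's Schedule of Assessments covers a culture-negative relapse within 90 days of end of treatment and within 11 months of randomization. In that case "treatment with the study drug will be re-started according to the treatment schedule" and visits restart. Box XII (Protocol 5.3.3) treats an exacerbation of inflammation as distinct from relapse, yet "if anti-amoebic treatment had been stopped restart this when anti-inflammatory treatment is re-started". Box XI adds: "Relapse within 11 months, after an initial response is common".

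**Testing.** SAP 7.9.3 makes time-to-cure the one secondary efficacy variable with formal testing. SAP 7.1.7 declares it significant if its p-value plus the primary p-value is below an overall level, for which no number is given. SAP 5.1 uses two-sided 0.10. SAP 7.1.1 sets two-sided 5% unless stated otherwise.

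**The concern.** A time-to-event variable should date the event that is being counted. Here the counted event is a resolution that held, while the date belongs to the first one recorded. For a subject who relapsed and was re-treated, the recorded time leaves out the relapse and the second course. The arm with more such subjects looks faster than it was.

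The level matters for a different reason. If alpha is chosen after the p-values are known, the same data can support or refuse the only formal secondary efficacy claim. The sum rule also demands more of time-to-cure than control of the error rate requires.

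**Working it through.** **1. Design figure.** The documents give no event count, hazard ratio or power for time-to-cure, so the design sample size is the figure to reproduce. Inputs (SAP 5.1): 63% vs 83%, two-sided alpha 0.10, 80% power, 10% loss.

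n per arm = (1.645 + 0.842)² × (0.63×0.37 + 0.83×0.17) / 0.20² = 6.18 × 0.3742 / 0.04 = 57.8, so 58. Total 116 evaluable; 116/0.9 = 129, against 130 stated. With 67% vs 87% the formula gives 52 per arm, and 104/0.9 = 116, as stated. The 58 per arm is used below.

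**2. The dating rule on one assumed subject.** First Yes on day 90, culture-negative relapse on day 120, second Yes on day 240, no later relapse. The subject is a CRR_12 success. The SAP dates cure at day 90; the resolution that held was on day 240. The gap is 240 − 90 = 150 days. SAP 7.2 sets the first possible status visit ("those who did not reach the day 30 visit, the first visit where disease status is recorded"), so the gap cannot exceed 365 − 30 = 335 days.

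**3. Size across a trial (simulation; every share is an assumption).** 58 per arm; exponential times to lasting cure giving 63% and 83% by month 12, read at monthly visits; two-sided log-rank for time-to-cure; two-sample linear model for CRR_12. Affected cures are dated 2 or 4 months early with equal chance, and left alone if that would precede month 1.

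| Affected cures, control vs test | Sum-rule power, alpha 0.10 | Cox hazard ratio for cure | Control cures dated early by (mean) |
|---|---|---|---|
| none | 71% | 1.72 | 0 days |
| 10% vs 0% | 70% | 1.69 | 6 days |
| 20% vs 5% | 69% | 1.67 | 11 days |
| 30% vs 10% | 68% | 1.65 | 17 days |

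With equal shares of 10, 20 or 30% in both arms, power stays within about 0.5 points of 71%. Two harsher variants use the same unequal shares. Moving otherwise-too-early dates to month 1 gives 67 to 69%. Drawing affected cures only from month 3 on gives 66 to 69%.

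With equal true CRR (63, 73 or 83%) and the same unequal shares, the sum rule wrongly declares the more-relapsing arm faster in 2.2 to 2.6% of trials, against a nominal 5% per side.

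**4. The unnamed level.** The room left for time-to-cure is alpha minus the primary p. With primary p = 0.04 it is 0.05 − 0.04 = 0.01, or 0.10 − 0.04 = 0.06. With primary p = 0.06 it is nothing, or 0.04.

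**5. Sum rule against fixed sequence.** If p₁ + p₂ < alpha, then p₁ < alpha and p₂ < alpha. The sum rule's rejection region is a triangle inside the square of a fixed sequence that tests both at full alpha. Both control error: a time-to-cure claim always implies a significant primary test, and never occurs unless p₂ < alpha. In the same simulation with correct dating (correlation of the two tests 0.92), power is about 71% (sum) vs 77% (fixed) at 0.10, and 61% vs 67% at 0.05. Under first-Yes dating and equal CRR, wrong-direction claims with the fixed sequence at 0.10 are 3.4 to 4.4%, still below 5%.

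**The case against.** **The dating effect depends on an assumed imbalance.** This stands. The Protocol calls relapse after an initial response common, but that is wider than relapse after resolution, and no rate is given for either. At equal shares the bias nearly vanishes. Tie handling, which the SAP does not specify, matters about as much: the continuous-time hazard ratio is ln(0.17)/ln(0.37) = 1.78, and monthly grouping with Breslow ties already brings it to about 1.72. None of this makes the first Yes the right date.

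**A reader might infer that event status is open**, so that a subject who resolved, relapsed and failed could count as cured. SAP 7.9.3 speaks of patients "classified as Cured at some point of time while in the study", and 8.3 censors those who did not experience clinical resolution. The SAP as a whole does not support that inference. Sections 3.1 and 6.1 build freedom from relapse into the definition of resolution. Section 7.9.1 dates only 12-month successes and treats discontinued subjects as not cured. The wording of 7.9.3 and 8.3 is loose, but the definition is there.

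**A reader might also infer that the differing censoring dates and time origins matter.** Censoring is at the last cure-status assessment in 7.9.3 and at completion or withdrawal in 8.3. Protocol 4.4 asks for end-of-study assessments at discontinuation where possible, so the two dates often coincide. With 10% loss and a lag of 1 to 3 months, power changes by at most 0.4 points. First dose follows randomization on Day 0, and the extra day in 8.5 is a constant, which cannot alter a Cox or log-rank result.

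**The sum rule is valid.** It is. Preferring a fixed sequence rests on power and on having one stated level, not on an error in the rule.

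**Conclusion.** Two things should change. First, SAP 7.9.1 and 7.1.7 misdate any success that needed re-treatment. In the main simulation the cost is about 1 to 3 points of power and a hazard ratio of 1.65 to 1.69 instead of 1.72. The loss reaches about 5 points in the harshest variant and is close to zero if re-treatment is equally common in both arms. These sizes rest on assumed shares and on exponential cure times at 63% vs 83%.

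Second, the level in 7.1.7 is not named and could be read as 0.05 or 0.10. This can change the verdict on time-to-cure. The sum rule itself gives up about 6 points of power to a fixed sequence.

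It would be too strong to say that first-Yes dating inflates formal error: under the SAP's own rule, wrong-direction claims stay below the nominal rate. The point concerns a secondary hypothesis. The primary CRR_12 analysis and the sample size are untouched.

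**What to change.** 1. **SAP 7.9.1 and 7.1.7, dating.** For CRR_12 successes, date cure at the earliest CRYN = Yes visit that is not followed by a recorded relapse or a restart of anti-amoebic therapy. If a success had a restart and no later Yes, as can happen after a Box XII exacerbation, use the first follow-up visit after the final end of treatment that confirms resolution. Keep first-Yes dating as a sensitivity analysis.
2. **SAP 7.1.7, testing.** Replace the sum rule with a fixed sequence: test time-to-cure at one alpha, stated as a number and equal to that of the primary difference test, only if that test shows superiority. The downside is that wrong-direction claims rise slightly but stay below the nominal level. No claim is lost when superiority fails, because the sum rule, applied to the difference test, already blocks it.
3. **SAP 7.9.3 and 8.3, tidying only.** Align both with 7.9.1: a subject who is not a CRR_12 success is censored whatever the earlier CRYN answers, at the last cure-status assessment, with randomization as origin.

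The cost is a few sentences and minor reprogramming before the code is broken. CRYN and RELAPYN are already collected. The SAP names no variable for restart dates, so confirm that they can be derived from the eCRF or the dispensing records kept under Protocol 5.7.
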